14. PRIVACY AND CONFIDENTIALITY OF SUBJECTS AND RESEARCH DATA

Data collected during this study will be obtained for research purposes and derived from study procedures. Data will be captured using a dedicated website containing a number of electronic case report forms (eCRF's). Data captured is de-identified upon entry. Identifiable information on individual subjects will be accessible only to the investigators and study staff. Electronic data will be de-identified and stored securely in a password protected EDC system maintained by the Clinical Cardiology Research Center (CCRC) at the University of Rochester. Study coordination, database management, and statistical analysis will be performed by CCRC. Research data will be stored indefinitely. All study binders with subject data will be stored securely in the locked Clinical Cardiology research offices. A paper enrollment log will be maintained in Regulatory binder and stored securely in the locked Clinical Cardiology Research offices.

Once the study is closed, all patient binders and regulatory binders will be boxed up, labeled (so easily identified), and taken to a specific locked storage room that all study files are kept.

Datos App: This is smart device app used via the subject's personal smart device. Password or PIN number is required for use of the app. Data transferred from Datos server running on

the Google Cloud Platform located on the East coast of the US and is encrypted. The use of this app and data transmissions have been vetted by University of Rochester IT.

15. DATA / SAMPLE STORAGE FOR FUTURE USE

Data will be stored with the UR research system for future use and used for research purposes and identified using study subject number. Data will be stored indefinitely. The PI and authorized research personnel working on the project will have access to the data. Restricted areas of any study website will be protected by user login. University of Rochester is protected by a dedicated firewall limiting the traffic source and type entering the University, which imposes restrictions on network protocols to reduce the risk of common vulnerabilities. SQL Server relational database enables central management, data acquisition, and data flow coordination and is used to design, manipulate, and protect data and build applications. Using a journaling audit trail option, we will track data changes. Prior to merging or extracting any data into or from the database, merge/extraction routines will be developed and thoroughly tested.

Blood samples for future research.

Purpose of blood samples.

Patients will have the option of providing blood sample for future research.

The study will collect blood samples and these will be stored at the University of Rochester at the time of enrollment for future research use, indefinitely. Providing blood samples for future research is optional for subjects. Samples will be stored at the University of Rochester Medical Center, but may also be sent to specialized labs for future genetic research with initial plans to assess polymorphisms and mutation in alpha and beta-adrenergic receptors systems, G-protein signaling pathways, ion-channelopathies, markers of fibrosis, myocardial damage, inflammatory markers and genetic biomarkers to determine their contribution to the individual patient response or lack of response to guideline directed medical therapies. These analyses will be exploratory and purposefully not included in the primary specific aims in light of limited data supporting their usefulness in predicting clinical events.

Description of the repository

In subjects who consent to blood sample collection, 3 tubes of blood will be collected at baseline. The samples will be de-identified and are to be labeled with the subject ID number given at enrollment, an anonymous bar code from the blood sample kit, and the date collected. The University of Rochester Central Laboratory will store the samples in a -80°C environment. The blood samples are coded and linked to a study key with subject identifiers which is protected from non-study personnel and will allow correlation of clinical data with biomarkers in the future. Subjects will not be contacted for the future use of their samples, nor will they be informed of the results of the research on their donated specimens.

Risks and Benefits

There is a very slight but small risk that the subject donating a sample could be identified. The risk is mitigated by coding the sample with the study subject ID number and use of an anonymous code. Subjects will be informed that contributing an anonymous specimen offers no direct benefit to subjects, nor will they be informed of any results.

16. DATA AND SAFETY MONITORING PLAN

An adverse event is any unexpected symptom, sign, illness, or experience that develops or worsens during the course of the study and is possibly or definitely related to study procedures.

Adverse Event Reporting

Investigators shall report to their local IRB, and report in the electronic data collection system within five business days of PI awareness only real or suspected, serious and unanticipated adverse events that are related to participation in the study (i.e. anaphylaxis to medication) Events related to standard of care such as medications side effects do not need to be reported unless severe as defined below. Death of a subject must be reported as an adverse event, per the serious adverse event definition below. The PI is aware that investigators are responsible for reporting to and following the guidance of any other applicable oversight bodies, including the Institutional Review Board (IRB).

Serious Adverse Event Definition

This population is at baseline increased risk of heart failure, death, and poor clinical outcomes. A serious adverse event is defined as any adverse medical experience that results in any of the following outcomes:

- death;
- is life-threatening;
- requires inpatient hospitalization or prolongation of existing hospitalization;
- results in permanent impairment of a body structure or a body function;
- requires medical or surgical intervention to prevent permanent impairment or damage;
- leads to fetal distress, fetal death or a congenital abnormality or birth defect.

Data Safety Monitoring Board

A data and safety monitoring board (DSMB) will be appointed to independently monitor the conduct and the outcome of the trial. The DSMB will be responsible for monitoring the safety and well-being of the patients participating in this study and ensuring the ethical conduct of the trial. Since this study is a pilot project enrolling approximately 30 patients using data already routinely used by clinicians and since the safety endpoints focus on optimizing current standard of care medications, the main focus of DSMB activity will be to monitor for potential increase in unexpected complications during the trial. For patients in the conventional treatment arm, data on clinical events including adverse events, cardiovascular hospitalizations, and death will also be collected and provided to the DSMB for evaluation of risks associated with drug therapy.

The board will meet every three months either in-person or via conference call to review the data. The DSMB will consist of 2 physicians with expertise in cardiology and one expert in biostatistics.

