Addition or removal of heart failure medications and changes in medication dosage will be left to the discretion of the treating physician. Upon completion of 6 month follow up the subjects will no longer require study visits and will return study equipment. We plan to collect study data from the electronic health record through 12 months at which time no further data will be collected.

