7. STUDY PROCEDURES

After consent, subjects will undergo/agree to the following study-related procedures (Consent and Enrollment may be done at separate visits):

- Garmin wearable wristband is provided for daily wear. Subjects should wear the wristband as often as possible. Subjects will return the Garmin wristband at 6 months.
- Quality of life questionnaire: KCCQ and a 3-question weekly electronic survey (e-survey) will be completed via the commercially-available Datos app platform. The survey

asks questions about how you are feeling, have you felt any symptoms, and the quality of your health status. The KCCQ should take 10 minutes to complete and the 3-question weekly e-survey should take 3 minutes to complete. Research staff will follow up with subject if weekly e-survey has not been completed for 2 weeks. REDCap may also be used as an alternative.

- Electronic medical record data regarding clinical history, medications, device implantation, and follow-up data will be collected for 12-month period.
- PROMIS data collected from medical record for 12 months, ICD data, medications, and other office visits/ hospitalizations/ unplanned visits standard of care will be available for chart review.
- Will participate in virtual visits, with phone visits occurring in the event a virtual visit is not possible. For those subjects in the intervention group, medications will be adjusted to optimize to medical guidelines; for those in the control group, no medications will be adjusted, but the subject will have the opportunity to share any changes in their medical status and any questions for the study staff. The control group will only receive their usual care and will not have their medications optimized by the research team. Visit time is approximately 30 minutes.
- Virtual Visit Overview with Subjects: Study staff will provide basic instruction to the subject on the use of Zoom. Study staff will show subject an example of a Zoom virtual visit to help them better understand the Zoom program before the first monthly virtual visit. Subjects will be invited, via e-mail link, to the Zoom meeting from the URMC HIPAA secured Zoom portal. They will then click on the invite link and will be directly connected with the study staff member. The Zoom Help Center (<https://support.zoom.us/hc/en-us>) may also be used as an online resource to help troubleshoot the virtual visit.

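### The adverse event definition in section 16 is not arm-neutral, so the plan does not give the DSMB the control-arm record of non-serious drug harms that it says the board will use

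*Combined protocol and SAP*

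**What the plan says.** Section 16 (Data and Safety Monitoring Plan) limits adverse events to unexpected occurrences and adds that the event "develops or worsens during the course of the study and is possibly or definitely related to study procedures". In its DSMB paragraph, the same section says that control-arm clinical events, adverse events among them, are "provided to the DSMB for evaluation of risks associated with drug therapy". It makes a rise in unforeseen complications the board's main focus.

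Whether a drug change is a study procedure depends on the arm. Section 7 (Study Procedures) says: "For those subjects in the intervention group, medications will be adjusted to optimize to medical guidelines". The same sentence continues: "for those in the control group, no medications will be adjusted". Section 4, under the control group, says: "Addition or removal of heart failure medications and changes in medication dosage will be left to the discretion of the treating physician".

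Three other sentences in section 16 bear on what is captured:

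- Side effects: "Events related to standard of care such as medications side effects do not need to be reported unless severe as defined below". No arm is named.
- Serious events: "A serious adverse event is defined as any adverse medical experience that results in any of the following outcomes". This sentence has no relatedness condition.
- Deaths: "Death of a subject must be reported as an adverse event".

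**The concern.** A control arm is useful for safety because it shows how often bradycardia, hypotension or kidney problems occur in similar patients who take the same drug classes without the intervention. That needs one definition applied in the same way to both arms. Here the definition turns on a link to study procedures, and those procedures differ by arm in exactly the respect that matters, namely who changes the drugs.

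Section 2 says the trial will show that managing patients with device data is safe, and the DSMB is asked to watch for a rise in complications. A rise can be judged only against a background rate. If the control background is thinned by the definition, a non-serious drug harm in the intervention arm may look like an effect of the strategy when it is ordinary for these drugs. If such harms are reported in neither arm, the board cannot assess them at all.

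**Working it through.** The plan gives no figure on this point, so there is none to reproduce. The check sets the passages side by side and then gives an illustration.

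**Step 1. Follow one event through the rules.** Take an unexpected, non-serious drug harm after a dose change.

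| Reading of section 16 | Change by study team (intervention) | Change by treating physician (control) |
|---|---|---|
| A. Definition taken literally, side-effect exemption not applied | Can be an adverse event: the change is a study procedure | Not an adverse event: the change is not a study procedure |
| B. Exemption for non-severe standard-of-care side effects applied to both arms | Need not be reported | Need not be reported |
| C. DSMB sentence taken to override the definition | Reported | Reported, but nothing in the definition says so |

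Reading A is asymmetric. Reading B is symmetric, but leaves the board without data on these harms. Only reading C delivers what the DSMB sentence promises, and it requires setting the written definition aside.

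**Step 2. What is captured on any reading.** Control deaths and cardiovascular hospitalizations are listed separately for the DSMB, whatever their cause.

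**Step 3. What is captured on one reading only.** The serious adverse event sentence covers any adverse medical experience with a listed outcome, which would include a control patient's non-cardiovascular admission. Against that, a serious adverse event can be read as a subset of adverse events. The five-day rule for the IRB and the data system is also limited to events related to taking part in the study. The exemption refers to events severe as defined below, but what follows defines serious. The text does not settle these cases.

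**Step 4. Illustration of size.** Inputs from the documents: about 30 patients at 2:1 (section 4.1), so 20 intervention and 10 control. Assumed, because the documents give neither: a true drug-harm risk r over 6 months, equal in both arms, and a share s of control harms that is captured. All intervention-arm harms are assumed to be counted.

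- Expected intervention count = 20r
- Expected control count = 10r in truth, 10rs as recorded
- Apparent risk difference = 20r/20 - 10rs/10 = r(1-s), when the true difference is 0

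| r | Intervention count | True control count | Difference at s = 0 | s = 0.25 | s = 0.5 | s = 1 |
|---|---|---|---|---|---|---|
| 10% | 2 | 1 | 10 points | 7.5 | 5 | 0 |
| 20% | 4 | 2 | 20 points | 15 | 10 | 0 |
| 30% | 6 | 3 | 30 points | 22.5 | 15 | 0 |

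This applies to reading A. Under reading B the artefact is zero for non-severe events, because neither arm records them.

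**Step 5. Would it look like a signal?** In the extreme case s = 0, sum the binomial(20, r) probabilities of intervention counts x for which Fisher's exact test of x/20 against 0/10 gives p of 0.05 or less. The result is 0.04%, 3.2% and 22.8% for r = 10%, 20% and 30%. The plan specifies no such test; this only gauges how striking an artefact could be.

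**The case against.** The strongest reply is that section 16 already limits the asymmetry. The side-effect exemption names no arm, and sections 8 and 11 describe the study's drug changes as standard of care, so non-severe side effects are arguably exempt in the intervention arm too. The definition also requires the event to be unexpected in both arms, and many beta-blocker or diuretic effects are foreseeable. Serious events are defined without relatedness. The list of control data for the DSMB is introduced as non-exhaustive. Under section 4, control patients are asked monthly about symptoms, drug changes by their own physician and adverse events, and new events are noted at 3 and 6 months. On this view the wording is loose, but the data will exist.

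Much of this stands. A reader might infer that no control drug harm can ever qualify, that the board's comparison is biased by definition, or that nearly all control drug harms are lost, giving counts such as 2 v 0 or 6 v 0. The documents do not support those statements. Deaths and cardiovascular hospitalizations are captured regardless of cause, and other serious or severe events have a plausible route in. No harm test or stopping boundary is specified, so a claim that the board would act on a false excess is conjecture. The zero counts come from assuming zero control capture.

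The reply does not remove the conflict. Applying the exemption to both arms makes the rule fair by leaving the board without non-severe drug-harm data. Asking control patients about adverse events does not help if the answers are then screened by a definition they cannot meet.

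**Conclusion.** The point holds in a limited form. The definition is not arm-neutral and does not fit the stated use of control adverse events to evaluate drug risk. For unexpected, non-serious drug harms, the written rules give either one-sided counting or no reporting in either arm, and neither provides a comparable control background.

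The size is unknown. With equal true risk and full counting in the intervention arm, the spurious difference is r(1-s). It ranges from 0 at full control capture to r at none, for example 5 to 15 points at s = 0.5 for assumed risks of 10% to 30%. It is zero for non-severe events if the exemption is applied to both arms. Where an artefact exists, it runs against the intervention. The primary endpoint is not affected. The change is worth making because it is cheap and the safety record of a pilot this small is easily misread.

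**What to change.** Amend section 16 as follows.

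1. For DSMB and trial reporting, remove the relatedness condition from the adverse event definition and record relatedness as a separate field.
2. In both arms, record clinically detected adverse events and all serious adverse events, regardless of attribution or of who changed the drug.
3. Tabulate them for the DSMB by randomised arm.
4. Keep the relatedness filter only for expedited IRB reporting.
5. Reconcile the side-effect exemption with the DSMB sentence, and say whether severe there means serious as defined.
6. Section 7 describes study blood tests only for the intervention arm, after diuretic changes. Flag laboratory-detected kidney or electrolyte events as unequally ascertained, and do not compare them directly between arms.

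The cost is a wording amendment and a few more event entries for about 30 patients, drawn from contacts and record review already planned in both arms. No visit, test or treatment changes. Unequal laboratory detection remains, which is why item 6 asks for a caveat and not a comparison.

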Patients are randomized 2:1 into:

An Intervention Group

The clinical management of the intervention group will be comprised of the following:

- A study care-team, comprised of a Cardiologist, an Electrophysiologist, a Registered Nurse, and study coordinator who will receive monthly physiologic and functional reports derived from Medtronic CIEDs incorporating Cardiac Compass and OptiVol monitoring.

- The study team will also be provided with patient-specific data derived from patient reported outcomes that include symptoms, quality of life scores, and PROMIS data if available. PROMIS®, a tool developed for use by the National Institutes of Health provides quality of life data, and is part of standard clinical care at the University of Rochester Medical Center Cardiology Department for patients. This is a survey patients have the option of filling out at clinic visits and available through the electronic medical record.
- The Datos app platform will be used to conduct a separate Quality of Life study survey and weekly e-survey REDCap may also be used as an additional resource..
- A pre-specified management regimen based on standard clinical practice will be provided to the study team in which medical management including medication dosing (focusing on beta-blockers and diuretics) will be monitored and modified using CIED and OptiVol data (see Figure 1 and footnote* at end of document). This is based on current and accepted clinical practice.
- The study team will contact the patients on a monthly basis for 4 monthly virtual visits. Based on CIED and patient engagement data, the study team will adjust medications and dosages, and optimize activity/ exercise steps. All medication changes resulting from the virtual visits will be updated in the subject's electronic medical record and communicated by medical chart messaging or URMC email based on the patient physician's preference.
- All study team contacts with the patients will be virtual, using telecommunication or E-communication. These options include URMC approved Zoom portal (currently used for URMC telemedicine clinical care), phone, or email. If the telemedicine call (preferred method) is disconnected, phone or email will be utilized. These e-communications will occur using an existing HIPAA compliant platform to improve efficiency, patient engagement, and reduce study costs while preserving data quality.

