- Blood samples may be taken as part of the study if a subject is randomized to the intervention group and the study team adjusts diuretic medications as clinically indicated. These blood samples are for patient safety and are routinely ordered to assess kidney function when a patient is taking diuretics. Labs will be ordered via a paper requisition and billed to the study. Research study staff will follow up within 3 days of result return.
- Future Use Blood Sample (optional)

Method of Assigning Subjects to Treatment

Study enrollment using the electronic data capture system that is available 24/7 to all study personnel. Patients will be randomized in a 2:1 fashion to either intervention or conventional management. Randomization will be conducted using a computer random number generator.

Follow-up Schedule (See also Table 1)

Following enrollment, all subjects will have scheduled follow-up visits (phone, electronic or telemedicine) by the study team at monthly intervals following enrollment and baseline testing.

CIED-derived physiologic and functional reports will be available to the study team only for patients assigned to the GDMT-medical optimization intervention group.

All subjects will be followed for a time-period of 6-months. Medical record data will be collected for a 12-month period.

The following time-points will be assessed:

- *Enrollment (V0):* Baseline clinical characteristics, existing echocardiographic measures and NYHA class will be recorded. Additional tests will include a 6-minute walk test and KCCQ questionnaire. Garmin wristband is provided.
- *Randomization (V1):* subjects will be randomized to an intervention arm of CIED-based medical optimization vs. conventional management.
- *Monthly virtual visits by research team (V1a):*
 - Conventional group: questions about symptoms, changes in activity levels, medications and adverse events. No additional CIED data provided to the subjects' usual clinical care providers since they will follow their own standard routine for CIED-monitoring.
 - Intervention group: virtual visits for medical optimization and prescription changes to medications based on CIED-reports and decision flowchart.
- *3-months (V2):*
 - Intervention group: office visit for clinical assessment, including physical exam and NYHA class. Clinical and adverse events.
 - Control group: office visit for device interrogation, medical record review, report any changes in standard care, NYHA class.
- *6-months (V3):*

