17. DATA ANALYSIS PLAN

Statistical Methods

Primary Statistical Hypothesis

To test the hypothesis that a multidisciplinary team intervention using pre-specified medication

dosing regimens guided by Cardiac Compass-Optivol data will increase the rate of change in beta-blocker and/or diuretic prescription (defined as initiation, termination, or dose adjustment) in the intervention group compared to usual care at 6 months.

Statistical Test Method and Sample Size Considerations

The primary outcome of this study is the rate of change in medical optimization (changes in heart failure medications and dosing) guided by CIED physiologic and patient engagement app data that are used together with pre-specified medication dosing regimens over 6 months. The rate of change in HF medications (beta-blocker, diuretic, and Sacubitril/Valsartan) will be compared between the multidisciplinary team intervention guided by CIED physiologic digital data group and usual care control group using chi-square analysis. We estimate that the rate of medication change will be 10% in the conventional group based on our URMC ICD database, as compared to 60% in the intervention group. Accordingly, a sample of approximately 30 patients will be required to provide a power of 80% and a 2-sided alpha of 0.05, accounting for 10% drop out rate. The comparison of the rate of recurrent medication adjustments between the two study groups will be assessed using negative binomial regression analysis and is expected to result in greater than 80% power (possibly 99%) based on the expected rate of multiple medical changes (at the monthly virtual visits) in the intervention group.

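### Nothing in the documents requires non-serious drug side effects to be entered, and at the virtual visits adverse-event questions are listed for controls only

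*Combined protocol and SAP*

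**What the plan says.** **Reporting rule.** Section 16 (Adverse Event Reporting) tells investigators to report to the IRB and to "report in the electronic data collection system within five business days of PI awareness only real or suspected, serious and unanticipated adverse events", provided that they are related to taking part. It then says: "Events related to standard of care such as medications side effects do not need to be reported unless severe as defined below". The definition that follows is of a serious adverse event; severe is not defined.

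**Adverse-event definition.** The same section opens by defining an adverse event as something unexpected that is at least possibly due to study procedures.

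**DSMB.** Adverse events, cardiovascular hospitalizations and deaths in the conventional arm are also to be collected and "provided to the DSMB for evaluation of risks associated with drug therapy".

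**Visit content.** For the intervention arm, Section 4 describes four monthly virtual visits and says: "Based on CIED and patient engagement data, the study team will adjust medications and dosages". Section 17 relies on the "expected rate of multiple medical changes (at the monthly virtual visits) in the intervention group". The Section 7 entry for those visits mentions optimization and prescription changes and nothing on adverse events. The entry for the other arm reads: "Conventional group: questions about symptoms, changes in activity levels, medications and adverse events". Section 4 gives controls the same adverse-event question. For the intervention arm, Section 7 lists adverse events at months 3 and 6 only.

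**The concern.** The intervention consists of drug adjustment by the study team, and Section 8 names medication side effects as a risk. The side effects most likely to follow a dose change are known and non-serious. These are the events that the reporting rule exempts and that the adverse-event definition can leave out. The written visit content also differs by arm, and the item is absent from the visits at which the team acts on drugs. If staff follow the text, the DSMB is asked to weigh drug risk with side-effect data that were gathered differently in the two groups.

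**Working it through.** The plan gives no figure to reproduce on this point. The check is a reading of the rule and a count of the schedule.

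**Step 1: two readings of the reporting sentence (Section 16).**
- If it governs all entry in the data system, non-serious drug side effects are left out.
- If it governs only the five-business-day expedited report, routine capture is left to other text. Section 14 mentions electronic case report forms but not their content. Section 8 promises monitoring for adverse effects but attaches no form, visit or recording rule. Section 7 provides chart review, medication lists and a three-question weekly survey, none of which is set out as side-effect recording.

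Under either reading, no statement in the documents requires a non-serious side effect to be entered.

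**Step 2: where an adverse-event item is listed after randomization.** Virtual visits fall at months 1, 2, 4 and 5, and clinic visits at months 3 and 6 (schedule table, Section 7).

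| Contact | Intervention | Control |
|---|---|---|
| Months 1, 2, 4, 5 | not listed (Sections 4, 7) | listed (Sections 4, 7) |
| Months 3, 6 | listed (Section 7) | not listed in Section 7; Section 4 lists new events |
| Row in schedule table | none | none |

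- Virtual visits: intervention 0 of 4, control 4 of 4.
- All contacts, intervention: 0 + 2 = 2 of 6.
- All contacts, control: 4 + 0 = 4 of 6 by Section 7, or 4 + 2 = 6 of 6 if new events in Section 4 include adverse events.
- Contacts at which both arms have the item: 0 of 6, or 2 of 6 on the wider reading.

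Brevity alone does not explain the difference, because the same Section 7 list does name adverse events for the intervention arm at months 3 and 6.

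**Step 3: the two parts together.** Even where adverse events are listed, the Section 16 definition can exclude an expected effect of a standard drug, in either arm. Equalizing the visit list would therefore not be enough; the definition and the capture rule need attention too.

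**Step 4: workload of a common form.** 30 patients × 6 contacts = 180 forms.

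**The case against.** The strongest reply is that the reporting sentence carries a five-day clock and names the IRB, so it reads as an expedited rule. Section 16 itself separates collection from reporting when it says that control-arm events will also go to the DSMB, which implies that intervention-arm events go there too. This stands as a reason to call the rule ambiguous. It does not supply a requirement to record non-serious side effects.

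Second, the plan gives a reason for modest safety collection. This is a pilot of about 30 patients using data already in routine use, and "since the safety endpoints focus on optimizing current standard of care medications", so the DSMB's main focus is a rise in unexpected complications. That is a fair design choice and limits how much can be asked. The same section nevertheless also gives the DSMB the evaluation of drug-therapy risk.

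Third, safeguards exist. Symptoms inform intervention-arm drug decisions (Section 4 and the flowchart in Section 7), monitoring is promised (Section 8), and extra contact after a dose change is allowed (Section 7). Records are reviewed for 12 months, and unplanned visits, hospitalizations and deaths are outcomes. These narrow the gap considerably. None provides a common record of non-serious side effects.

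A reader might infer more from the planning rates. Section 17 assumes that the "rate of medication change will be 10% in the conventional group based on our URMC ICD database, as compared to 60" per cent in the intervention group. With about 20 and 10 patients this gives 0.60 × 20 = 12 and 0.10 × 10 = 1, so most patients with a drug change are in the arm without the item at virtual visits. That only restates the planned treatment effect, and Section 4 also allows changes at months 3 and 6, where the item is listed. It does not measure missed events. Nor do the contact counts, since they record where an item is written and not what clinicians ask.

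**Conclusion.** The point holds as a cheap improvement. As written, capture of non-serious drug side effects is not required, and the listed adverse-event inquiry differs by arm: 0 of 4 virtual visits in the intervention arm against 4 of 4 in controls. The resulting data would not be comparable for the DSMB's evaluation of drug-therapy risk.

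This rests on the text being followed as written and on no unseen case report form already covering the gap.

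Two stronger readings are not supported. The intervention arm is not without safety oversight, given the month 3 and 6 items and the safeguards above. It also cannot be said that the intervention would look safer than it is: symptom review might reveal more events in that arm, and the absent item might reveal fewer. The documents show neither the size nor the direction of any bias. The mismatch between severe and serious is a wording point.

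**What to change.** - Keep the expedited reporting rule, and state separately what is recorded in the data system.
- Use one identical adverse-event form in both arms at all six scheduled contacts. It should cover expected medication side effects and the reason for each drug change. The reason is useful because the primary endpoint in Section 4 counts terminations and dose adjustments alike, whatever prompted them.
- Add an adverse-event row to the schedule table in Section 7.
- Reconcile Sections 4, 7 and 16: the virtual-visit content by arm, new events against adverse events, severe against serious, and the definition of an adverse event.
- Tabulate events by arm for the DSMB, descriptively. Show study-ordered kidney results separately as intervention-arm only, since Section 7 provides for them only in that arm.

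No visits or patients are added. The cost is one form, one table row, some wording, and the entry of about 180 short forms.
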